## SUMMARY OF CHANGES

### Protocol Amendment #6

#### **LCCC1841: A Pilot Study of Acalabrutinib in Relapsed/Refractory Primary and Secondary CNS Lymphomas**

##### **AMENDMENT INCORPORATES:**

- ☒ Editorial, administrative changes
- ☐ Scientific changes
- ☐ Therapy changes
- ☐ Eligibility Changes

**Rationale for amendment:** The purpose of this amendment is to clarify the status of Acalabrutinib. AstraZeneca is providing a commercial supply of this drug for this study and the study is IND exempt, and therefore the references in the protocol to investigational drug have been updated.

##### **Editorial, administrative changes:**

Throughout Sections	Removed language referring to an Investigator's Brochure
Sections 1.4	Removed language referring to Acalabrutinib as investigational
Section 4.1.10	Removed language referring to Acalabrutinib as investigational
Section 5.2	Removed language referring to a Medical Monitor
Section 6.1	Removed language referring to Acalabrutinib as investigational
Section 9.1.3	Removed language referring to Acalabrutinib as investigational
Section 13.1	Updated the URL for prohibited medication list in Appendix A

***THE ATTACHED VERSION DATED 25 NOVEMBER, 2024 INCORPORATES THE ABOVE REVISIONS***

## SUMMARY OF CHANGES

### Protocol Amendment #5

#### **LCCC1841: A Pilot Study of Acalabrutinib in Relapsed/Refractory Primary and Secondary CNS Lymphomas**

##### **AMENDMENT INCORPORATES:**

- ☐ Editorial, administrative changes
- ☒ Scientific changes
- ☐ Therapy changes
- ☒ Eligibility Changes

**Rationale for amendment:** The purpose of this amendment is to clarify that MYD88 and CXCR4 testing of tumor samples is optional, dependent on availability of tissue. Furthermore, eligibility criteria has been updated so that subjects who are currently receiving investigational treatments or have received an investigational agent within 28 days prior to dosing are not eligible for this study.

##### **Scientific changes:**

- Section 7.4.3 Testing of tumor sample clarified as optional if available.
- Section 8.1 Time and events table and footnote 17 updated to clarify that tumor sample testing is optional if available.

##### **Eligibility changes:**

- Section 4.2.3 Exclusion criteria updated to state that subjects should not currently be receiving investigational treatment or have received an investigational agent within 28 days of dosing.

***THE ATTACHED VERSION DATED July 26, 2023 INCORPORATES THE ABOVE REVISIONS***

## SUMMARY OF CHANGES

### Protocol Amendment #4

#### **LCCC1841: A Pilot Study of Acalabrutinib in Relapsed/Refractory Primary and Secondary CNS Lymphomas**

##### **AMENDMENT INCORPORATES:**

- ☒ Editorial, administrative changes
- ☒ Scientific changes
- ☐ Therapy changes
- ☒ Eligibility Changes

**Rationale for amendment:** The purpose of this amendment is to remove antifungal prophylaxis from the protocol. Isavuconazole is cost prohibitive to the subject and evidence does not support antifungal prophylaxis in this setting.

##### **Editorial, administrative changes:**

Mechanical edits made as needed.

##### **Scientific changes:**

- Section 1.5      Removed rationale for isavuconazole
- Section 1.5.1.1      Removed reference to isavuconazole relative to dose justification.
- Section 1.5.1.2      Removed isavuconazole section
- Objective 2.3.2      Removed isavuconazole from the objective.
- Section 5.1      Removed isavuconazole reference in schema and from Table 1.
- Sections 5.2, 5.3      Removed isavuconazole
- Section 6.2      Removed isavuconazole drug section
- Section 8.1      Removed isavuconazole from the Time and Events Table and removed associated footnote 15.
- Section 13.5      Removed reference to isavuconazole in the patient handout.
- Appendix E

##### **Eligibility changes:**

- Criterion 4.1.10      Removed inclusion criterion.
- Criteria 4.2.8      Removed isavuconazole from the criteria and 4.2.16

***THE ATTACHED VERSION DATED March 20, 2023 INCORPORATES THE ABOVE REVISIONS***

## SUMMARY OF CHANGES

Protocol Amendment #3
------------------------------

### **LCCC1841: A Pilot Study of Acalabrutinib in Relapsed/Refractory Primary and Secondary CNS Lymphomas**

#### **AMENDMENT INCORPORATES:**

- ☒ Editorial, administrative changes
- ☒ Scientific changes
- ☐ Therapy changes
- ☒ Eligibility Changes

**Rationale for amendment:** The purpose of this amendment is to include the tablet form of acalabrutinib to the treatment plan. Eligibility was also updated given that the capsule form of acalabrutinib prohibits the enrollment of subjects who are currently being treated with acid reducing agents. Now the eligibility also states that the tablet form of acalabrutinib can be co-administered with all acid reducing agents. Drug information was updated throughout the protocol to account for both capsule and tablet forms of acalabrutinib. Honest broker language was also added to the protocol.

#### **Editorial, administrative changes:**

- Section 7.4 Honest broker language added
- Mechanical edits made throughout.

#### **Scientific changes:**

- Section 6.1 Acalabrutinib tablet details added
- Section 6.1 Storage conditions for Acalabrutinib tablet and capsule updated to 20°C-25°C (68°F-77°F) with excursions permitted to 15°C-30°C (59°F-86°F)
- Section 6.1 Language for identified and potentials risks associated with Acalabrutinib updated.

#### **Eligibility changes:**

- Section 4.2.10 Exclusion criteria updated to allow for enrollment of subjects on acalabrutinib tablets and the co-administration of acid reducing agents.

***THE ATTACHED VERSION DATED October 19, 2022 INCORPORATES THE ABOVE REVISIONS***

**PROTOCOL AMENDMENT #2**

**LCCC1841: A Pilot Study of Acalabrutinib in Relapsed/Refractory Primary and Secondary CNS Lymphomas**

**AMENDMENT INCORPORATES (check all that apply):**

- X Editorial, administrative changes
  - Scientific changes (IRB approval)
- X Therapy changes (IRB approval)
- X Eligibility Changes (IRB approval)

The primary purpose of this protocol amendment is to update the eligibility criteria as it pertains to subjects with prior or current malignancies. A clarification regarding Hy's law was also added within the adverse events section.

**Editorial/Administrative**

1. Minor edits made where appropriate.

**Therapy**

1. A section about Hy's law was added to Section 9.2.

**Eligibility**

2. Criterion 4.1.11 was added to clarify eligibility for subjects with prior or current malignancies and in turn, the previous exclusion criterion 4.2.5 was removed.

***THE ATTACHED VERSION January 27, 2022 INCORPORATES THE ABOVE REVISIONS***  
**ATTACH TO THE FRONT OF EVERY COPY OF PROTOCOL**

## PROTOCOL AMENDMENT #1

### **LCCC1841: A Pilot Study of Acalabrutinib in Relapsed/Refractory Primary and Secondary CNS Lymphomas**

#### **AMENDMENT INCORPORATES (check all that apply):**

- X Editorial, administrative changes
- X Scientific changes (IRB approval)
  - Therapy changes (IRB approval)
- X Eligibility Changes (IRB approval)

The primary purpose of this protocol amendment is to change the study design from a Phase 2 Simon Two-stage study to a pilot study. Given the rarity of the disease and the accrual goal of 28 patients, the study is not feasible to complete the study in a timely fashion. The definition for the evaluability for toxicity was edited to indicate that toxicity evaluation begins with the first dose of acalabrutinib as it is the first drug administered. Additional administrative changes were made to clarify the dosing of isavuconazole, to change the funding source from Acerta Pharma to AstraZeneca, and to update language related to acalabrutinib relative to the package insert and investigator's brochure.

#### **Editorial/Administrative**

2. Mechanical edits made where appropriate.
3. Title changed to "Pilot Study."
4. Section 1.4 was updated to provide updated study and risk information for acalabrutinib.
5. A typo in the dosing for isavuconazole was corrected in section 1.5.1.2
6. The funding source on the protocol title page is changed to AstraZeneca from Acerta Pharma B.V.
7. Section 5.2: Table 2. Acalabrutinib Dose Modifications. Updated with current package insert information.
8. Section 5.3: Added vaccine guidance for the study.
9. Section 6.1: Updated acalabrutinib drug information and risks
10. Section 9.3.3: Language added to align with section 9.1.2.
11. Section 9.4.2 updated with new funding source name and information.
12. Appendix I: Added to include highly effective contraceptive methods

#### **Scientific**

1. Section 1.1: The change from a Phase 2, Simon Two-stage study was described.
2. Sections 1.1, 8.4, 10.3: Updated to clarify the number of evaluable subjects to be recruited.
3. Section 5.0:

- a. Schema was modified to include the number of evaluable subjects to be recruited.
  - b. The description of the study was modified to tailor it to the new pilot design.
  - c. Figure 2 is deleted as it is no longer relevant.
4. Sections 8.3 and 5.2 were edited for consistency to indicate that evaluability for toxicity will begin with the first dose of acalabrutinib since it is the first study drug given.
5. Section 10 is updated to provide details of the new study design.
  - a. Section 10.1: Study design is updated.
  - b. Section 10.2: Sample size, accrual time, and statistical power is updated.
  - c. Section 10.3 Addition of sample size.

### **Eligibility**

3. Criterion 4.1.1 was added to eligibility and in turn, the previous exclusion criterion 4.2.24 was removed.
4. Criterion 4.1.2: Criterion was updated.
5. Criterion 4.1.11 was updated.
6. Criterion 4.2.5: Updated to add carcinoma in situ of the prostate
7. Criterion 4.2.22: Updated criterion
8. Criterion 4.2.24: Added criterion to allow the investigator to exclude a subject with a disease that may make it undesirable for a subject to participate in the study.
9. Criterion 4.2.25: Added to exclude subjects with progressive PML
10. Criterion 4.2.26: Added to exclude subjects receiving live vaccine within 28 days of the first dose of study drug
11. Criterion 4.2.27: Added to exclude subjects with significant infection
12. Criterion 4.2.28: Added to exclude subjects in a concurrent clinical trial
13. Criterion 4.2.29: Added to exclude subjects with life-threatening illness or conditions or other conditions that may increase the risk to the subject or study.

## LIST OF ABBREVIATIONS

AE	Adverse event
AESI	Adverse event of special interest
AIHA	Autoimmune hemolytic anemia
ALP	Alkaline phosphatase
ALT	Alanine aminotransferase
AST	Aspartate aminotransferase
AUC	Area under the curve
BCR	B-cell receptor
BCRP	Breast cancer resistance protein
BID	Bis in die (twice daily)
BTK	Bruton's tyrosine kinase
CAP	College of American Pathologists
CBCD	Complete blood count with differential
CL/F	Oral clearance
CLIA	Clinical Laboratory Improvement Amendments
CLL	Chronic lymphocytic leukemia
Cmax	The maximum concentration of a drug in the body after dosing
CMP	Comprehensive metabolic panel
CNS	Central nervous system
CPO	Clinical Protocol Office
CR	Complete response
CRF	Case report form
Cru	Complete response/unconfirmed
CSF	Cerebrospinal fluid
CV	Curriculum vitae
CXCR	C-X-C chemokine receptor
CYP3A	Cytochrome P450 Family 3 Subfamily A
DLBCL	Diffuse large B-cell lymphoma
DoR	Duration of response
DSMB	Data and Safety Monitoring Board
DSMC	Data and Safety Monitoring Committee
ECOG	Eastern Cooperative Oncology Group
eCRF	Electronic case report form
FDA	Food and Drug Administration
FDG	Fludeoxyglucose
GCP	Good Clinical Practice
HBs-Ag	Hepatitis B surface antigen
HBc	Hepatitis B core
HBV	Hepatitis B virus
HCV	Hepatitis C virus
HIPAA	Health Insurance Portability and Accountability Act
HIV	Human immunodeficiency virus
IDS	Investigational Drug Service
IEC	Institutional Ethics Committee
IL	interleukin
IRB	Institutional Review Board
ITP	Immune thrombocytopenic purpura
K	potassium
LCCC	Lineberger Comprehensive Cancer Center
LDH	Lactate dehydrogenase
MCL	Mantle cell lymphoma
Mg	Milligram

MMSE	Mini-Mental Status Examination
MRI	Magnetic resonance imaging
Na	Sodium
NC TraCS	North Carolina Translational and Clinical Sciences Institute
NCI	National Cancer Institute
NCI-CTCAE	National Cancer Institute – Common Terminology Criteria for Adverse Events
NFkB	Nuclear Factor kappa-light-chain enhancer of activated B cells
NK	Natural killer
NYHA	New York Heart Association
OHRE	Office of Human Research Ethics
ORR	Overall response rate
OS	Overall survival
PCNSL	Primary central nervous system lymphoma
PD	Progressive disease
PET	Positron emission tomography
PFS	Progression free survival
PI	Principal investigator
PCNSL	Primary CNS lymphoma
PCR	Polymerase chain reaction
PR	Partial response
PRC	Protocol review committee
Rb	Rubidium
RSNA	Radiological Society of North America
SAE	Serious adverse event
SAR	Suspected adverse reaction
SCNSL	Secondary central nervous system lymphoma
SD	Stable disease
SRS	Stereotactic radiosurgery
SUV	Standardized uptake value
TLR	Toll-like receptor
Tmax	The time after administration of a drug when the maximum plasma concentration is reached
TPF	Tissue Procurement Facility
ULN	Upper limit of normal
UNC	University of North Carolina
UNC-CH	University of North Carolina- Chapel Hill
UP	Unanticipated problem
USP	United States Pharmacopeia
Vss	Mean steady-state volume of distribution
WBRT	Whole-brain radiotherapy

## 1.0 BACKGROUND AND RATIONALE

### 1.1 Study Synopsis

LCCC 1841 is a multicenter open-label, single-arm, pilot study designed to investigate the antitumor effects of acalabrutinib in subjects with relapsed primary central nervous system lymphoma (PCNSL), and relapsed secondary CNS lymphoma (SCNSL) with no evidence of current systemic disease. Subjects with the following histological subtypes of lymphoma will be included in the study: diffuse large B-cell lymphoma (DLBCL, all subtypes); mantle cell lymphoma (MCL, all subtypes); plasmablastic lymphoma, and lymphoplasmacytic lymphoma. Up to 16 subjects will receive acalabrutinib at the dose of 100 mg approximately every 12 hours (See Study Schema) to attain a total of 15 evaluable subjects as defined in Section 8.4. If the study shows a positive effect of acalabrutinib in treating CNS lymphomas, acalabrutinib could become the standard relapsed CNS lymphoma regimen, not only for PCNSL, but also in certain subtypes of SCNSL. Any complete responses to acalabrutinib treatment will be clinically notable as spontaneous remissions do not occur.

In a previous study, ibrutinib showed a CR rate of 45% and an ORR of 68% [1]; in another study [2], ibrutinib showed a CR rate of 17% and an ORR of 55%. Thus, in order to recommend further investigation of acalabrutinib as a regimen for primary CNS lymphoma, acalabrutinib treatment must show an overall response rate (ORR) of at least 70%, which would demonstrate that it is not inferior to previously approved regimens.

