## 10.0 STATISTICAL CONSIDERATIONS

### 10.1 Study Design

As the first study of acalabrutinib in relapsed/refractory CNS lymphoma, LCCC1841 study is designed as an open label, single arm pilot study to provide preliminary data about its efficacy before proceeding to a larger two arm study. Furthermore, since this is a rare lymphoma, it would take an unreasonable amount of time and multiple centers would be needed to enroll an adequate number of subjects for a randomized phase 3 study.

The null hypothesis is:  $H_0: \text{ORR} \leq 50\%$  vs  $H_1: \text{ORR} \geq 70\%$  (i.e., 20% improvement). We plan to obtain 15 evaluable patients in this pilot study.

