### 10.2 Sample Size, Accrual and Duration of Accrual

We plan to accrue up to 16 subjects to ensure planned (evaluable, in terms of status of overall response) sample size of 15. With 15 evaluable subjects, we reject the null hypothesis when we observe  $> 9$  (10 or more) responders. This design gives power 72% with one-sided type 1 error 0.15. We will replace non-evaluable (e.g., loss to follow-up) cases by new subjects to guarantee planned sample size.

Accrual for this trial is expected to take approximately 24-36 months.

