### 10.3 Data Analysis Plans

Analysis of efficacy will be conducted following pre-specified inference rule on rejecting the null hypothesis:  $H_0: \text{ORR} \leq 50\%$ . Specifically, we will reject the null hypothesis if and only if there are  $>9$  ORs in the 15 subjects. The main analysis is inferential because we frame it as a hypothesis-testing problem. We will also calculate 2-sided 95% clopper-Pearson confidence interval for ORR.

Secondary endpoints include PFS, CR, DoR, overall survival, and safety/toxicity. Analyses of secondary endpoints will be descriptive. Specifically, time-to-event outcomes like PFS, DoR, and OS will be analyzed using Kaplan-Meier method, and Kaplan-Meier survival curves will be provided. Categorical outcomes like CR, and safety/toxicity (different types of AEs) will be summarized using frequencies.

- For the primary outcome, ORR, there should be no missing data. We will replace non-evaluable cases with new subjects so that the total sample size of 15 evaluable subjects is guaranteed.
- There is only one test for the primary endpoint and hence there is no multiplicity issue.

Per exploratory endpoints:

[REDACTED]

[REDACTED]

[REDACTED]

[REDACTED]

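### Sections 1.1 and 10.3 set different go-forward rules (at least 70%, against 10 of 15), and the non-inferiority claim in Section 1.1 has nothing in the design behind it

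*Combined protocol and SAP*

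**What the plan says.** The formal rule is in Section 10. Section 10.1 sets a null ORR of at most 50% against an alternative of at least 70% and fixes the sample size: "We plan to obtain 15 evaluable patients in this pilot study". Section 10.3 gives the decision rule: "we will reject the null hypothesis if and only if there are $>9$ ORs in the 15 subjects". Section 10.2 gives the operating characteristics: "This design gives power 72% with one-sided type 1 error 0.15". Section 10.3 then adds an estimate: "We will also calculate 2-sided 95% clopper-Pearson confidence interval for ORR".

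Section 1.1 gives a separate condition for recommending further study. After citing two ibrutinib reports with ORRs of 68% and 55%, it says that "acalabrutinib treatment must show an overall response rate (ORR) of at least 70%, which would demonstrate that it is not inferior" to regimens approved earlier. It does not mention the count of 10, the 50% null or any margin.

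Section 10.1 describes the trial as an "open label, single arm pilot study to provide preliminary data about its efficacy before proceeding to a larger two arm study".

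**The concern.** The trial exists to inform one decision: whether acalabrutinib goes on to a larger study. Two sections state the condition for that decision, and they do not give the same number. A result that meets one and fails the other would let readers choose the verdict after seeing the data. The power in Section 10.2 would also be quoted for a decision that Section 1.1 makes by a stricter rule.

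The second issue is the inference attached to the 70% figure. Section 1.1 treats reaching it as a demonstration of non-inferiority. The only planned test compares a single arm with a fixed 50%. A report that followed the synopsis could claim comparability with ibrutinib that the design was never set up to assess.

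**Working it through.** **Inputs.** n = 15, p0 = 0.50 and p1 = 0.70 (Section 10.1); reject at 10 or more responders (Sections 10.2 and 10.3); go-forward condition of at least 70%, and ibrutinib ORRs of 55% and 68% (Section 1.1); two-sided 95% Clopper-Pearson interval (Section 10.3).

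**Step 1: reproduce the plan's figures.** For X ~ Binomial(15, p), P(X ≥ r) = Σ C(15,k) p^k (1−p)^(15−k), summed over k = r to 15.

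- Type I error at r = 10: (3003 + 1365 + 455 + 105 + 15 + 1)/32768 = 4944/32768 = 0.1509.
- Power at r = 10: P(X=10) + P(X=11) + P(X≥12) at p = 0.7 = 0.2061 + 0.2186 + 0.2969 = 0.7216.

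Both agree with the stated 0.15 and 72% at the precision given.

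**Step 2: turn 70% into a count.** 0.70 × 15 = 10.5, so the smallest count meeting it is 11 (11/15 = 73.3%). Ten responders give 66.7%, which falls short.

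**Step 3: operating characteristics of the two rules.**

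| Rule | Observed ORR at the threshold | Type I error (ORR 50%) | Power (ORR 70%) |
|---|---|---|---|
| 10 or more (Section 10.3) | 66.7% | 4944/32768 = 0.1509 | 0.7216 |
| 11 or more (Section 1.1, observed rate) | 73.3% | 1941/32768 = 0.0592 | 0.2186 + 0.2969 = 0.5155 |

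**Step 4: how often the rules disagree.** They disagree only at X = 10. At a true ORR of 70%, P(X=10) = 0.2061, and 0.2061/0.7216 = 29% of rejections. At a true ORR of 50%, P(X=10) = 3003/32768 = 0.092.

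**Step 5: what the 70% condition can support.** The Clopper-Pearson limits are the 0.025 quantile of Beta(r, 16−r) and the 0.975 quantile of Beta(r+1, 15−r).

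- 10/15: 38.4% to 88.2%.
- 11/15: 44.9% to 92.2%.

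At 11/15, the first result that meets the 70% condition, the lower limit is 55 − 44.9 = 10.1 points below one cited ibrutinib ORR and 68 − 44.9 = 23.1 points below the other. A non-inferiority statement at this level would need a margin larger than those gaps, even if the reference rates were treated as known constants. The plan states no margin.

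**The case against.** **The 70% may only restate the alternative.** Section 10.1 uses the same figure for the alternative hypothesis, so Section 1.1 could be a loose reference to the target rate. This is a fair reservation, and the 11/15 count depends on it. But the sentence says what the treatment must show before further study is recommended, which most naturally means the observed rate. On the other reading it still needs rewording, because rejecting an ORR of at most 50% does not establish a true ORR of 70%. The 95% lower limit is 68.05% at 14/15 and 78.2% at 15/15, so only 15 of 15 would exclude rates below 70%.

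**Section 10 is sound on its own terms.** This stands. Its rule, power and error agree with one another, the rules conflict at a single count, and this is a pilot. The defect lies in Section 1.1 and its mismatch with Section 10.

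**Stronger readings that the documents do not support.**

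- A reader might infer a third bar at 12/15, the first count at which the 95% interval (51.9% to 95.7%) excludes 50%. Section 10.3 attaches no success criterion to the interval. It is an additional estimate.
- A reader might say the type I error is misstated because it is 0.1509. It rounds to the stated 0.15, and the rule is a count, so no decision changes.
- A reader might argue that a 50% null below both ibrutinib rates rules out non-inferiority. A non-inferiority null always lies below the reference by the margin. Rejecting 50% would correspond to a 5-point margin against a fixed 55%, or an 18-point margin against a fixed 68%. Similarly, a one-sided 85% lower bound at 11/15 is 56.8%, above 55% though not above 68%. The claim is therefore unsupported rather than proven false: the plan never chooses a margin, a reference rate or a confidence level for it.

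**Conclusion.** Wrong as written, on two counts.

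First, the two go-forward conditions conflict at 10/15, a result that a drug at the target rate produces about one time in five. The published power applies to the more lenient condition; under the stricter one, a drug with a true ORR of 70% would fail almost half the time (1 − 0.5155 = 0.48). These figures assume exactly 15 evaluable subjects and that 70% refers to the observed rate.

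Second, the statement that 70% would demonstrate non-inferiority does not follow from anything in the design. This does not depend on how the 70% is read, since no margin, concurrent comparator or non-inferiority test appears anywhere in the plan.

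The Section 10 test itself needs no correction.

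**What to change.** In Section 1.1, replace the 70% sentence with wording such as: *At least 10 responders among 15 evaluable subjects rejects ORR ≤ 50% and supports further investigation.* If the sponsor does intend the 70% bar, change the rule in Sections 10.2 and 10.3 to 11 or more of 15 and restate power as 52% and one-sided type I error as 0.059.

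In either case, delete the non-inferiority claim. The ibrutinib rates can stay as context.

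Optionally, label the 95% interval in Section 10.3 as descriptive, because at 10/15 and 11/15 it includes 50% although the test rejects.

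Keeping the 10/15 rule costs only wording and a more modest synopsis claim, with no added subjects or procedures. Choosing 11/15 costs about 21 percentage points of power at the present sample size (0.7216 − 0.5155 = 0.206). Either change should be made before the response results are known.
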